Patients with ALL on Total XVI or "as per TOTXVI" who experience NP/PN after specific doses of vincristine are eligible to enroll in the study as soon as the diagnosis of NP/PN related to VCR is established. The qualifying doses of vincristine have been selected because they fall in the schedule of weekly vincristine doses as per Total XVI, and 2 additional weekly vincristine doses are anticipated according to the protocol. Participants will be randomized to receive gabapentin or placebo upon enrollment. Morphine will be available to both groups as needed for pain at any time on the study. At the time of enrollment, and daily thereafter until completion of the study drug, data will be collected for pain assessment, and the daily dose of oral morphine used will be collected. Data regarding the pain type, quality, and location, as well as treatments used to manage pain will be assessed on a daily basis for the diagnostic event and for the period following the next two administrations of VCR treated with the study drug.

Objectives:

Primary Objective:

To assess the analgesic efficacy of gabapentin in controlling VCR-related NP/PN in participants with ALL, by comparing the morphine daily dose (mg/kg/day) used to control NP/PN as a primary or a rescue regimen in the gabapentin vs. placebo groups.

Secondary Objective:

To compare the pain scores in the gabapentin and placebo groups as recorded by pain score right now and pain score average for previous 24 hours.

Responsible Investigator: [name]

Statistician: [name].

Estimated date for completion of data collection: December 2015

TINALL - Therapeutic Interventions for Peripheral Neuropathy/Neuropathic Pain Induced by Vincristine Treatment for Childhood ALL on Total XVI Protocol

Hypotheses/Estimates: The hypothesis is that treatment with gabapentin has better analgesic efficacy than placebo in the treatment of VCR-related NP/PN. Based on the current enrollment on the Total XVI protocol, the projected enrollment, the incidence of NP/PN of 34.9% as determined in our previous study of NP/PN associated with the Total XV protocol, we estimate that 60 study participants will be eligible to enroll in this study during the duration of the Total XVI study. To achieve a total of 60 evaluable patients, up to 80 participants may be enrolled.

Criteria for Evaluation:

Safety: Any adverse events will be recorded and reported.

Efficacy: Efficacy will be evaluated based on two outcome measures: the daily dose of oral morphine used as needed for pain (mg/kg/day) and the pain scores daily, during the treatment course with either gabapentin or placebo.

Study Design: Randomized placebo controlled phase II study**Study Population:**

Inclusion Criteria:

1. Participant is enrolled on Total XVI or “as per TOTXVI”.
2. **Participant is 1 year of age or older.**
3. Participant has symptoms of NP/PN with onset no more than 7 days after one of the following vincristine doses dates \pm 3 days: protocol week 1, week 2 (induction), week 7 (reinduction I), or week 17 (reinduction II).
4. Patient is expected to receive 2 doses of vincristine in weekly intervals as outlined by the Total XVI or “as per TOTXVI” protocol while on study drug (i.e. no known dosage reductions or planned missed doses).
5. Participant is able and willing to take oral medications.

Exclusion Criteria:

1. Previous participation in this study
2. Participant is receiving gabapentin for another indication at the time of diagnosis of NP/PN or has received gabapentin previously.
3. Pregnancy. Female participants of childbearing potential must have documented negative urine or serum pregnancy test result not older than 7 days. Male patients with reproductive potential will be counseled not to procreate during the study.
4. **Impaired renal function: decreased eGFR (< 60ml/min/1.73m² as estimated by the Schwartz equation).**
5. Participant has allergy or other contraindication for either morphine or gabapentin therapy.
6. Inability or unwillingness of research participant or legal

TINALL - Therapeutic Interventions for Peripheral Neuropathy/Neuropathic Pain Induced by Vincristine Treatment for Childhood ALL on Total XVI Protocol

guardian/representative to give written informed consent.

Sample Size: The sample size will depend on the incidence of NP/PN in the eligible population. Based on our retrospective data from Total XV, we expect a sample size of 60, with 30 to be randomized to the gabapentin arm or the placebo arm, respectively. However we will enroll and randomize all eligible and consented patients in the remainder of Total XVI. To achieve a total of 60 evaluable patients, up to 80 participants may be enrolled.

Randomization: Patients with ALL on Total XVI or “as per TOTXVI” who experience NP/PN after certain doses of vincristine are eligible to enroll in the study as soon as the diagnosis of NP/PN related to VCR is established. Participants will be randomized to receive gabapentin or placebo and continue taking the study drug until 2 doses of vincristine have been completed, and for 7 days after the second dose of vincristine. Morphine will be available to both groups as needed for pain at any time on the study.

Data Analyses: Two efficacy measurements will be analyzed: the average daily morphine dosage and the average daily pain score during the maximum 21-day treatment period. We will test the null hypothesis that the expected average daily morphine dosage and pain score are the same in the gabapentin and the placebo group vs. a one-sided hypothesis that the expected average daily morphine dosages and pain scores are lower in the gabapentin group.

Anticipated Primary Completion Date: December 2016

Anticipated Study Completion Date: December 2018

Timeframe for Primary Outcome Measure:

Data Management: Data management and statistical analysis will be provided locally by the Department of Anesthesiology and Biostatistics Department at St. Jude Children’s Research Hospital, respectively.

Human Subjects: The risk to subjects is related to the side effects of gabapentin. The most common side effect is somnolence. Patients will be informed of this and other minor side effects during informed consent. Adverse events will be monitored and reported and treated appropriately.

Table of Contents

List of Collaborating Investigators/Institutions Protocol Summary

1.0	OBJECTIVES	1
1.1	Primary Objective.....	1
2.0	BACKGROUND AND RATIONALE	1
2.1	Background	1
2.2	Rationale.....	2
3.0	RESEARCH PARTICIPANT ELIGIBILITY CRITERIA AND STUDY ENROLLMENT	3
3.1	Inclusion Criteria.....	3
3.2	Exclusion Criteria.....	4
3.3	Research Participant Recruitment and Screening	4
3.4	Enrollment on Study.....	4
3.5	Procedures for Identifying and Randomizing Research Participant.....	5
4.0	TREATMENT PLAN	6
4.1	Study Treatment	7
4.2	Breakthrough Pain Control.....	7
4.3	Dose Modifications	8
4.4	Definitions of Dose-Limiting Toxicity.....	8
4.5	Concomitant Therapy	8
4.6	Supportive Care	8
5.0	DRUG INFORMATION	8
5.1	Gabapentin (Neurontin).....	8
5.2	Placebo.....	9
6.0	REQUIRED EVALUATIONS, TESTS, AND OBSERVATIONS	10
6.1	Pre-Study Evaluations	10
6.2	Evaluations during Therapy	10

Appendix I: Example of a schedule of evaluations

Appendix II: Research Activities

Appendix III: Pain Scales

1.0 **OBJECTIVES**

The investigators propose to study the analgesic efficacy of gabapentin for the treatment of neuropathic pain/peripheral neuropathy (NP/PN) associated with vincristine therapy in the context of treatment of childhood ALL on Total XVI protocol.

1.1 **Primary Objective**

To assess the analgesic efficacy of gabapentin in controlling VCR-related NP/PN in participants with ALL, by comparing the morphine daily dose (mg/kg/day) used to control NP/PN as a primary or a rescue regimen in the gabapentin vs. placebo groups.

1.2 **Secondary Objective**

To compare the pain scores in the gabapentin and placebo groups as recorded by pain score right now and pain score average for previous 24 hours.

2.0 **BACKGROUND AND RATIONALE**

2.1 **Background**

Children with cancer experience a significant symptom burden during the course of treatment^{1,2}, and pain is the most frequent, most severe and most distressful of symptoms. The impact of pain experienced during treatment for cancer has long term implications after completion of therapy^{3,4}.

Neuropathic pain and related neuropathy symptoms have been directly correlated with chemotherapeutic agents⁵, vincristine in particular⁶ and have been reported during therapy for childhood cancers^{7,8}.

Neurotoxicity, the dose-limiting side effect of vincristine, most often causes mixed sensorimotor neuropathy (loss of deep tendon reflexes, paresthesias, neuritic pain, and wrist or foot drop) or autonomic neuropathy (constipation, abdominal pain, paralytic ileus, bladder atony with retention of urine, and orthostatic hypotension). On the rare occasions in which vincristine-associated neurotoxicity involves the cranial nerves, it produces transient cortical blindness, oculomotor nerve dysfunction with ptosis and diplopia, jaw pain, facial palsy, hearing loss, and vocal cord paresis or paralysis⁵.

The incidence of peripheral neuropathy related to vincristine during treatment of childhood ALL per protocol Total XIIIB in our institutional experience has been 17.5% (42 of 240)⁹ and peripheral neuropathy/neuropathic pain were identified as adverse events in 34.9% of

children treated on protocol Total XV (174 of 498)¹⁰. Due to the higher vincristine dose used in our current institutional protocol for treatment of childhood ALL, Total XVI, and knowing that vincristine toxicity is related to higher individual doses as well as cumulative dose, we expect an even higher incidence during Total XVI treatment.

2.2 Rationale

Given the significance of the problem of neuropathic pain during cancer treatment in children, the associated suffering, and the long term impact, we propose to prospectively investigate the value of two therapeutic intervention arms for NP/PN, in children with ALL treated per Total XVI or “as per TOTXVI” protocol. Furthermore, our retrospective analysis did not demonstrate conclusively the analgesic efficacy of gabapentin, although clinical applications of gabapentin for VCR-neuropathy continue to persist with varying treatment regimens and despite the lack of data from relevant clinical trials.

The design of the study is a randomized placebo-controlled study, comparing a regimen based on opioid only to a regimen comprised of opioid and gabapentin. Existing data from clinical trials has failed to show the best treatment regimen to control or prevent VCR-induced NP/PN in children. There are indications in the literature in adult neuropathic pain syndromes such as diabetic neuropathy and postherpetic neuralgia that dual therapy of opioid and gabapentin has better analgesic efficacy than either individual therapy¹¹; nevertheless, no such investigations have explored therapies for neuropathic pain in children.

Rationale for dose selection and duration of gabapentin therapy

The gabapentin dose selection for this study is based on the data in the literature describing the clinical use of gabapentin in children with neuropathic pain¹²⁻¹⁹ and on our institutional experience with gabapentin in a retrospective study evaluating neuropathic pain in children with ALL during Total XV therapy¹⁰. There are no PK data supportive of gabapentin dose regimens for neuropathic pain in children.

Three case reports¹⁷⁻¹⁹ and 5 small series¹²⁻¹⁶ describe the use of gabapentin as an adjuvant analgesic in children with NP under diverse circumstances: after thoracotomy¹⁷, after multilevel orthopedic surgery¹⁴, and for complex regional pain syndrome^{15,18}, systemic lupus erythematosus¹³, cancer-related pain^{12,19}, neck pain¹², and phantom limb pain¹⁶. These studies included 24 children, and the dose regimen of gabapentin was described for only 17 of them^{12,14,16,17}. Analgesic efficacy was reported at 22.5 mg/kg/day in a 12-year-old with post-thoracotomy NP¹⁷, 14-40 mg/kg/day in 7 patients 7 to 28 years old with phantom limb pain¹⁶, 19-32.6 mg/kg/day in 4 children 11 to 17 years old with NP after

multilevel orthopedic surgery¹⁴, and 10-30 mg/kg/day in 5 children with cancer-related pain (n=4) or neuropathic neck pain (n=1)¹².

Dosing and safety information for the pediatric use of gabapentin has been defined only for anti-seizure therapy²⁰. Most pediatric pain specialists recommend the anti-seizure dose regimen for children with NP, starting at 10 mg/kg/day and titrating upward to 50 to 70 mg/kg/day. Gabapentin is currently the first-line therapy for NP at our institution. In our retrospective review of neuropathic pain during Total XV protocol for ALL at St. Jude, we found treatment data for 180 of 207 episodes of NP in 153 of 174 patients; the missing data reflect treatment at a site other than St. Jude. Gabapentin was used to treat 62.2% of episodes (112 of 180) in 65.4% of patients (100 of 153); the remaining 37.8% of episodes (68 of 180) in 34.6% of patients (53 of 153) were treated with opioids. The selection of gabapentin or opioids did not appear to be influenced by the pain intensity score at the time of diagnosis of NP (p=0.91). The mean starting dose used for the 112 episodes was 15.5 mg/kg/day (SD 7.9)¹⁰. In this study we found the median starting dose to be 14.2 mg/kg/day. In the absence of a uniform approach to the use of gabapentin, prospective studies are needed to determine the optimal regimen. There is some evidence that concurrent use of gabapentin and morphine provide better analgesia at doses lower than those used for single-agent therapy¹¹.

The duration of gabapentin therapy of up to 21 days is based on the pattern of administration of the trigger agent for neuropathic pain in ALL. We have selected the phases of the Total XVI or “as per TOTXVI” protocol during which VCR is administered most intensely, in weekly doses. Indeed, data from Total XV and preliminary data from Total XVI or “as per TOTXVI support the highest cumulative incidence of neuropathic pain at the time of induction, reinduction I and II. The duration of gabapentin therapy reflects the duration of vincristine administration.

3.0 RESEARCH PARTICIPANT ELIGIBILITY CRITERIA AND STUDY ENROLLMENT

According to institutional and NIH policy, the study will accession research participants regardless of gender and ethnic background. Institutional experience confirms broad representation in this regard.

3.1 Inclusion Criteria

- 3.1.1 Participant is enrolled on Total XVI
- 3.1.2 Participant is age 1 year or older.
- 3.1.3 Participant has symptoms of NP/PN with onset within 7 days after one of the following vincristine doses dates ± 3 days: protocol week 1 or week 2 (induction), week 7 (reinduction I), or week 17 (reinduction II).

- 3.1.4 Patient is expected to receive 2 weekly doses of vincristine as outlined by the Total XVI or “as per TOTXVI” protocol while on study drug (i.e. no known dosage reductions or planned missed doses).
- 3.1.5 Participant is able and willing to take oral medications.

3.2 **Exclusion Criteria**

- 3.2.1 Previous participation in this study
- 3.2.2 Participant is receiving gabapentin for another indication at the time of diagnosis of NP/PN or has received gabapentin previously
- 3.2.3 Pregnancy. Female participants of childbearing potential must have documented negative urine or serum pregnancy test result not older than 7 days. Male patients with reproductive potential will be counseled not to procreate during the study.
- 3.2.4 Decreased GFR (<60ml/min/1.73m² as estimated by the revised Schwartz equation^{21,22}).
- 3.2.5 Participant has allergy or other contraindication for morphine or gabapentin therapy.
- 3.2.6 Inability or unwillingness of research participant or legal guardian/representative to give written informed consent.

3.3 **Research Participant Recruitment and Screening**

Participants will be identified by referral to the study team (Pain Service) from the primary clinical team (Leukemia Service), upon diagnosis of NP/PN. In addition to referrals from the Leukemia Service, the study team will screen the clinical notes of potentially eligible Total XVI or “as per TOTXVI patients for documentation of new onset NP/PN and determine eligibility. With the agreement of the primary clinical team, a study team member will approach the potentially eligible participant to initiate informed consent discussions.

When informed consent is obtained and the patient is enrolled, a member of the study team will inform the pharmacy and the randomization procedure will be initiated. The pharmacy order sets will be activated for the study drug and open label oral morphine.

3.4 **Enrollment on Study at St. Jude**

A member of the study team will confirm potential participant eligibility as defined in Section 3.1-3.2, complete and sign the ‘Participant Eligibility

[figure not shown]
Checklist'. The study team will enter the eligibility checklist information into the Patient Protocol Manager (PPM) system. Eligibility will be reviewed, and a research participant-specific consent form and assent document (where applicable) will be generated. The complete signed consent/assent form(s) must be faxed to the CPDMO to complete the enrollment process.

The CPDMO is staffed 7:30 am-5:00 pm CST, Monday through Friday. A staff member is available by pager Saturday, Sunday, and holidays from 8:00 am to 5:00 pm.

3.5 Procedures for Identifying and Randomizing Research Participants

The PI or other study team member will approach the parent and participant regarding the study. If both the research participant and parent agree to participate, the randomization plan established by the study biostatistician will be accessed according to Section 11.

4.0 TREATMENT PLAN

*Qualifying VCR dose – dose falling on a weekly interval with at least 2 more weekly doses expected. Includes vincristine dose dates: Induction week 1 ± 3 days, Induction week 2 ± 3 days, Reinduction I (week 7) ± 3 days or Reinduction II (week 17) ± 3 days.

4.1 Study treatment

Upon each participant's enrollment, study staff will randomize the participant to one of 2 possible treatment arms (see section 11 for randomization procedure) and order the study treatment. The pharmacy will dispense a supply of the study treatment (gabapentin vs. placebo) sufficient to last through the end of the study (not more than 21 days), as well as the oral morphine for use as needed.

The pharmacy order will read "Gabapentin/Placebo study drug (TINALL)" and doses will be calculated as 20 mg/kg/day PO divided into 3 doses and rounded to the nearest 100 mg for capsules and 10 mg for liquid preparation. Neither the ordering clinician nor the participant / family will be informed of the treatment assignment.

Study treatment order entry will be managed by study staff according to pharmacy and institutional policy for medication administration. Any modifications to the study treatment (dose, duration, frequency, or discontinuation) will be done by the study team.

4.1.1 Active treatment arm

Participants randomized to the active treatment arm will receive gabapentin 20mg/kg/day PO divided into 3 doses and rounded to the nearest 100 mg for capsules and 10 mg for liquid preparation.

4.1.2 Placebo treatment arm

Participants randomized to the placebo treatment arm will receive look-alike capsules or liquid in a respective capsule size or liquid measure equivalent to the active treatment arm, but which contain no active treatment.

4.2 Breakthrough pain control

All participants, regardless of treatment assignment, will receive open-label oral morphine (0.15 mg/kg/dose every 2 hours, **rounded to the nearest tablet size or measurable liquid quantity**), as needed for pain. Morphine orders and dosages will be managed by the pain team according to clinical indication and following institutional and pharmacy policy for prescription and administration of controlled substances.

Substitution of other opioids for morphine should be avoided and performed only upon consultation with the PI.

4.3 Dose Modifications

The most common side effect of gabapentin is sedation/drowsiness. Participants who experience unacceptable side effects will have dosage adjustments at the discretion of the PI, or will be taken off therapy. If dose adjustment is indicated, study treatment will be reduced by 5-10 mg/kg/day.

Elimination of gabapentin can be affected by renal impairment which could increase drug exposure. Patients who are found to have renal impairment while on the study (defined as GFR < 60ml/min/1.73m² as estimated by the Schwartz equation^{21,22}) will be taken off therapy. Renal function of participants will be reviewed at least weekly while on study.

4.4 Definitions of Dose-Limiting Toxicity

The most common side effect of gabapentin is sedation/drowsiness. Participants who experience unacceptable side effects will have dosage adjustments or will be removed from the study (see section 4.3)

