6.4 Off-Study Evaluations

Patients will be off study when the patient has completed the study treatment and applicable pain assessments have been collected. If pain symptoms persist at the completion of the study, the patient will continue to be treated as needed, with gabapentin and/or morphine, either by the pain team or the leukemia team, but no additional data will be collected for this study.

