6.5 Long-Term Follow-up Evaluations

This study will not evaluate NP events or long term results beyond the off study evaluation.

Participants will be notified of their treatment assignment (gabapentin or placebo) after the completion of data collection for the last participant enrolled. Notification will be performed by a member of the study team in person (when feasible) or by letter at the earliest convenience of the study team and documented in the study files.

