7.2 Toxicity Evaluation Criteria

Participants who experience unacceptable side effects will have dosage adjustments or will be removed from the study (see section 4.4). The decision to adjust the study treatment dose or to discontinue study treatment will be made by the PI and in the context of the participant's clinical situation.

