8.0 CRITERIA FOR REMOVAL FROM PROTOCOL THERAPY AND OFF-STUDY CRITERIA

8.1 Off-study criteria

- 8.1.1 Completion of study therapy and assessments
- 8.1.2 Death
- 8.1.2 Lost to follow-up
- 8.1.3 Request of the Patient/Parent
- 8.1.4 Discretion of the Study PI, such as the following
 - The researcher decides that continuing in the study would be harmful
 - New information is learned that a better treatment is available, or that the study is not in the participant's best interest

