8.2 Off-therapy criteria

- 8.2.1 Development of unacceptable toxicity during treatment
- 8.2.2 Development of renal impairment, defined as GFR less than 60ml/min/1.73m² as estimated by the Schwartz equation^{21,22}.**
- 8.2.3 Refusal of therapy
- 8.2.4 Unblinding of participant or study team to participant's treatment assignment (see section 9.3)**

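### Toxicity stops are called both removal from the study and off therapy, and no section explicitly continues the daily assessments that the intent-to-treat analysis needs

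*Combined protocol and SAP*

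**What the plan says.** Four places deal with unacceptable side effects, and they name two different outcomes.

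- Section 4.4: "Participants who experience unacceptable side effects will have dosage adjustments or will be removed from the study (see section 4.3".
- Section 7.2, first sentence: such participants "will have dosage adjustments or will be removed from the study (see section 4.4". Its second sentence describes the choice as adjusting the dose or stopping treatment: the decision "to discontinue study treatment will be made by the PI".
- Section 4.3, to which 4.4 refers: they "will have dosage adjustments at the discretion of the PI, or will be taken off therapy".
- Section 8.2.1 lists "Development of unacceptable toxicity during treatment" as an off-therapy criterion. The separate off-study list in 8.1 begins with "Completion of study therapy and assessments" and does not name toxicity. Its nearest item is investigator discretion when continuing would be harmful.

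Nothing is planned once a child is off study. Section 6.5 says "This study will not evaluate NP events or long term results beyond the off study evaluation". Section 6.4 says "no additional data will be collected for this study", though that sentence is about children whose pain persists when the study is complete.

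Section 11.1 models daily morphine dose with a repeated-measures linear model and includes, by intent to treat, participants who were taken off study drug.

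**The concern.** The primary endpoint is the daily morphine dose. An intent-to-treat comparison of daily doses needs the days after a child stops study drug as well as the days before. If staff act on 4.4 and 7.2 as written, or on the sentences that link assessment to study drug, the morphine and pain days after a toxicity stop may never be recorded, and the reason would be related to treatment. The repeated-measures model would keep such a child with fewer records, so the child is not dropped. The comparison would, however, hold only that child's on-drug days.

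Handling could also differ between children. Staff who follow the morphine sentence in 6.2 and the appendices would go on collecting, and staff who follow 7.1 might not. Days that are not recorded at the time cannot be recovered at the analysis.

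**Working it through.** **Step 1: which outcome is meant.** Sections 4.4 and 7.2 (first sentence) say removal from the study. Sections 4.3, 8.2.1 and 7.2 (second sentence) mean stopping study drug. Since 4.4 cites 4.3 and 8.1 does not list toxicity, off therapy is the likelier intention. Read literally, 4.4 and 7.2 end data collection.

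**Step 2: what is collected if the child is off therapy but still on study.**

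| Tied to study drug | Not tied to study drug |
|---|---|
| Protocol summary, treatment outline: pain and morphine data collected daily up to the end of study drug | 6.2: daily morphine dose is collected for the duration of the study |
| Protocol summary, efficacy criteria: both measures evaluated over the treatment course | Appendix I: daily pain and adverse event assessment from enrolment to Day 21 |
| 6.2: daily pain assessment up to the end of study treatment | Appendix II: pain, opioid use and adverse events marked to day 21 |
| 7.1: daily assessments continue while on study drug, whatever the response | 8.1 and 8.2 are separate lists; 9.3 has unblinded patients followed off therapy |

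The right-hand column does not settle the question. Appendix I is headed as an example and puts the last dose of study drug on Day 21. Appendix II marks study drug on the same days as the assessments. Section 9.3 concerns unblinded patients and specifies only the status of the serious adverse event. For adverse events the gap is smaller: nothing ties the daily assessment to being on drug, and 9.1.2 still records related events.

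**Step 3: how many records are exposed.** The plan gives no figure to reproduce, so this is an illustration.

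Inputs: Appendix II counts days from the qualifying vincristine dose, with enrolment on day d = 1 to 7 and last day 21; 11.1 plans 30 children per arm. Assumptions: one stopped child, a stop on drug-day 5 or 10, collection ending with the drug, and the ±3-day dose window ignored.

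- Planned records per child: 22 − d, so 21 (d = 1) down to 15 (d = 7).
- Records lost: 22 − d − 5 = 17 − d for a stop on drug-day 5, and 22 − d − 10 = 12 − d for drug-day 10.
- Arm share: records lost ÷ (the child's planned records + those of the other 29 children, each with 15 to 21).

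| | Stop on drug-day 5 | Stop on drug-day 10 |
|---|---|---|
| Child's loss, d = 1 | 16/21 = 76% | 11/21 = 52% |
| Child's loss, d = 7 | 10/15 = 67% | 5/15 = 33% |
| Arm share, minimum | 10/(15 + 29×21) = 10/624 = 1.6% | 5/624 = 0.8% |
| Arm share, maximum | 16/(21 + 29×15) = 16/456 = 3.5% | 11/456 = 2.4% |
| Arm share, all enrolled on day 4 | 13/(30×18) = 13/540 = 2.4% | 8/540 = 1.5% |

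Drug-day 5 is study day d + 4, which is day 5 to day 11. That is always before the vincristine dose expected on day 14, so the whole period after that dose would be lost.

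**The case against.** The wording conflict largely resolves itself: 4.4 points to 4.3, the next sentence of 7.2 speaks of stopping treatment, and 8.2.1 governs. That stands, and it makes part of this point editorial.

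The stronger argument is that, on the off-therapy reading, the document as a whole leans towards continued follow-up. A child can be off drug and on study, 8.1.1 and 6.4 both join treatment with assessments, both appendices run to Day 21, and 11.1 presupposes data on children taken off drug. This is a reasonable reading, but it has to be inferred, and it runs against four sentences that link pain or morphine collection to study drug.

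Some of the adverse text should not be pressed too far. The 6.4 sentence concerns persistent pain at completion. The purpose of the 7.1 sentence is to keep assessing regardless of response. The summary also speaks of daily assessment after the next two vincristine doses, but qualifies those as doses treated with the study drug. As extracted, the Off Study column in Appendix II is marked on days 7 to 21, so exit before day 21 is contemplated; that does not say what an off-therapy child should have done.

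It is also true that impact is not shown. There is no stop rate, 4.3 allows dose reduction before stopping, and one stopped child costs an arm a small share of its records.

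Finally, the remedy reaches every off-therapy child under 8.2, including refusal and unblinding. That is wider than toxicity, but 11.1 makes no distinction by reason, and the off-study exits in 8.1 would still apply.

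**Conclusion.** The concern holds. The protocol names two different outcomes for the same toxicity trigger, and no section explicitly continues the daily morphine, pain and adverse event assessments after such a stop, while 11.1 relies on those children by intent to treat. The gap matters most for morphine and pain and less for adverse events.

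If collection ends with the drug, each stopped child loses between 33% and 76% of planned records, or 0.8% to 3.5% of a 30-child arm's records, in the two stop days examined. These figures rest on assumed stop days and one stopped child. The effect on the treatment estimate cannot be calculated, and neither unequal stopping between arms nor a direction of bias is established. This is not a fatal flaw, but it should be corrected.

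**What to change.** 1. In 4.4 and 7.2, replace removal from the study with taken off therapy, in line with 4.3 and 8.2.1.
2. In 6.2 and 7.1, add one sentence each: participants off therapy under 8.2 continue the daily adverse event, pain and morphine assessments to their planned last study day (7 days after the second vincristine dose, at most Day 21) unless consent is withdrawn, and these days enter the 11.1 model under the assigned arm.

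The decision whether to stop study drug is unchanged. The cost is two wording changes, two sentences and some extra contacts per stopped child: 10 to 16 for a stop on drug-day 5, and 5 to 11 for a stop on drug-day 10. Section 6.2 already allows pain assessment by phone.
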